5.3. Measurements of study drug compliance

Drug compliance will be presented using the off-site PPS.

5.3.1. Volume of the total bolus

The number of patients with actual total volume of IMPs equal and different (less or greater) from the theoretical one will also be presented by arm.

Moreover, the absolute (mL) and relative (%) differences between theoretical and actual volumes of IMPs will be presented quantitatively and qualitatively (in classes) by arm.

Theoretical volume will be calculated by multiplying the body weight measured at the V2 by 0.1 mL for Elucirem and 0.2 mL for Dotarem and rounded to the nearest integer.

The absolute difference will be calculated as follow: actual volume – theoretical volume.

CONFIDENTIAL	STATISTICAL ANALYSIS PLAN N° GDX-44-016 VERSION N° 4.0 (REF I011622)	F015830-03 Page 22 / 35
--------------	--	----------------------------

The relative difference will be calculated as follow: $\text{abs}(\text{actual volume} - \text{theoretical volume}) / \text{theoretical volume}$.

5.3.2. Volume of the preload bolus

The number of patients with a preload bolus will be tabulated by arm.

Listing of measurements of compliance with trial drug will be presented in CSR appendix 16.2.5.

5.4. Demographic and Other Baseline Characteristics

Demographic and other baseline characteristics (except clinical laboratory data) will be presented on the Off-site PPS and on the Off-site FAS. Clinical laboratory data will be presented on the Off-site PPS and on the SS.

5.4.1. Demographic data

Demographic parameters will be described per arm and overall, with descriptive statistics.

Listing of demographic data will be presented in CSR Appendix 16.2.4.

5.4.2. Study disease

The study disease and its characteristics (type, grade according to IWRS and e-CRF), the localisation of the tumour, the procedure documenting the study disease, the time between imaging procedure and first injection of IMPs (in months) and the time between imaging procedure and informed consent signature (in months) will be presented by arm and overall with descriptive statistics.

Listing related to study disease will be presented in CSR Appendix 16.2.4.

5.4.3. Medical history and concomitant diseases

Summary tables (number and % of patients) grouped by SOC and PT will be presented by arm and overall for medical history firstly then for concomitant diseases.

Tables will be sorted by descending frequency of SOC and, within each SOC, by descending frequency of PT according to the overall column.

The number and percentage of patients presenting with at least one Medical History under medication will be presented.

Listing of all diseases, with a flag for ongoing diseases will be presented in CSR Appendix 16.2.4.

5.4.4. Imaging history

Summary tables (number and % of patients) will be presented by arm and overall for previous exposure to gadolinium complex, number of examination(s) and occurrence of AE.

5.4.5. Prior medications and Procedures

Summary tables (number and % of patients) grouped by ATC codes (Version WHO Drug September 2024) will be presented for prior medications (those with “End of Treatment” coded 1) and by SOC and PT for prior procedures (those with “End Date” of the procedure inferior to the date of the IMPs administration).

The tables will be sorted according to the percentage of patients reporting at least one previous medication / at least one previous procedure from the most to the least frequent globally.

Listing of all medications and procedures will be presented in CSR Appendix 16.2.4.

CONFIDENTIAL	STATISTICAL ANALYSIS PLAN N° GDX-44-016 VERSION N° 4.0 (REF I011622)	F015830-03 Page 23 / 35
--------------	--	----------------------------

5.4.6. Clinical laboratory evaluation at baseline

Serum creatinine and eGFR data will be presented by arm using the Off-site PPS, Off-site FAS and SS. Time between blood drawing at V1 and MRI performed at V2 will be calculated as follow: (MRI date - blood drawing date in days).

Serum creatinine and eGFR data will be analysed quantitatively. eGFR will be also analysed qualitatively.

Quantitative analyses will be performed by tabulating the raw data.

Qualitative analysis of eGFR will present number of patients with value:

- <30 mL/min/1.73m²,
- ≥30 and <60 mL/min/1.73m²,
- ≥60 and <90 mL/min/1.73m²,
- ≥90 mL/min/1.73m².

Listing of all laboratory evaluation at baseline will be presented in CSR Appendix 16.2.8.

5.4.7. MRI examination

All the sequences performed during the MRI examination as well as the magnetic field strength (in Tesla) will be tabulated by arm.

Listing of MRI examinations will be presented in CSR Appendix 16.2.4.

5.4.8. Other baseline characteristics

For women with childbearing potential, summary table (number and % of patients) of the test performed or not and the result of the test will be displayed (positive, negative), at V1 and V2 (if V2 performed more than one day after V1), by arm and overall.

Listing of all other baseline characteristics will be presented in CSR Appendix 16.2.4.

5.5. Efficacy evaluation

Listing of all efficacy data will be presented in CSR appendix 16.2.6.

5.5.1. Primary analysis

The primary endpoint of the trial is the proportion of patients presenting with CBV map of excellent and good diagnostic quality, according to off-site readers, in the Elucirem® and the Dotarem® arm.

Technical adequacy of perfusion CBV map will be tabulated on the ARTPS, Off-site PPS and Off-site FAS, for each off-site reader, according to the following scale:

- non-diagnostic,
- poor,
- fair,
- good.

Of note, patients for whom the technical adequacy of perfusion CBV map will be assessed as “non-diagnostic”, by at least one off-site reader, will be excluded from the Off-site FAS and Off-site PPS.

For the perfusion CBV map that will be evaluated by the off-site readers, as technically non-diagnostic (artifacts that completely compromise the image interpretability), the major artifacts will be tabulated and presented for each off-site reader on the ARTPS:

- Movement artifacts,

CONFIDENTIAL	STATISTICAL ANALYSIS PLAN N° GDX-44-016 VERSION N° 4.0 (REF I011622)	F015830-03 Page 24 / 35
--------------	--	----------------------------

- T2* artifacts (any non-evaluable series like black series due to susceptibility issues linked to magnetic issues),
- EPI distortion,
- Other.

Non-inferiority will be assessed by calculating the difference in proportion of patients presenting with images of excellent and good diagnostic quality, after consensus between off-site readers, between Elucirem® and Dotarem® arms, and by constructing a two-sided 95% CI around this difference. If the lower bound of the two-sided 95% CI is above the pre-stated margin of non-inferiority (-12%), Elucirem® will be declared non-inferior to Dotarem®.

The Wald statistical test with a continuity correction will be used.

In case of conclusion of non-inferiority of Elucirem® compared to Dotarem®, the superiority of Elucirem® compared to Dotarem® will then be tested in the same way as described above for the non-inferiority (lower bound of the CI is above 0). No adjustment for multiplicity is needed as it is a simple closed testing procedure.

The primary analysis will be performed on the Off-site PPS and then on the Off-site FAS and presented by arm only on one hand, and by arm and grade assigned at randomization on the other hand.

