8.4 Off-Site Reading of Images

Off-site image evaluations are image evaluations performed at sites that have not otherwise been involved in the conduct of the trial and by readers who have not had contact with patients, investigators, or other individuals involved in the trial.

Images will be evaluated by prospective evaluation of the blinded images in a centralized manner. All images will be sent to an imaging core laboratory (ICL), which will prepare the images for evaluation. The file headers of all the images transmitted in DICOM format are to be edited to remove patient or site identification. For all images, any sequence information will be removed. Scalar information in the MR images will be preserved. A complete audit trail of any changes to the file headers will be maintained.

| | | |
|--|--|----------------------------|
|  CONFIDENTIAL | Protocol No. GDX-44-016 Version No. 1.0 - ITA Date 15 March 2023 | F015919-05 Page 34 / 59 |
|--|--|----------------------------|

The blinded image evaluations will be performed by 2 independent blinded readers experienced in brain tumor and perfusion imaging. In case of discordance, a consensus meeting will be organised in order to reach an agreement. The following criterion will be concerned by the consensus in case of discordance:

- The localization of the lesion
- The diagnostic quality of the CBV map (primary criterion).
- rCBV quantification (consensus in the glioma grade, not in the rCBV value)
- Visual evaluation of the T2* signal intensity time curve, including the confidence in the diagnosis.

An imaging eCRF will be used to ensure that the images and the diagnostic findings are properly aligned and to ensure that all data necessary for the trial purpose are documented by the independent blinded readers.

8.4.1 *Manuals and Supplies*

Guerbet (or the ICL) will document the imaging tasks and obligations of the investigational site in an Imaging Manual. As defined in [section 8.2](#), the standardized image acquisition guidelines or imaging protocol will be provided to the sites as part of the Imaging Manual.

In addition, the Imaging Manual will detail the steps required for masking confidential patient information and transferring images to the ICL (if applicable).

Guerbet (or the ICL) will document the central imaging process in a Blinded Imaging Evaluation Charter.

8.4.2 *Site Qualification*

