2.2. Efficacy criteria

CBV map is generated through a post-processing software for each DSC-MRI perfusion. Technical adequacy of perfusion CBV map is determined, by on-site and off-site readers (two readers blinded to the IMP), using a 4-point scale with the following grades:

- non-diagnostic,
- poor,
- fair,
- good.

CBV maps are considered technically non diagnostic if artifacts completely compromise image interpretability. Therefore, the assessment of primary and secondary criteria stops at this step.

The major artifacts are recorded as follows:

- Movement artifacts,
- T2* artifacts,
- Echo Planner Imaging (EPI) distortion,
- Other, to be specified.

Only for images considered technically adequate (i.e., poor, fair or good), the evaluation of primary and secondary criteria is performed.

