5.2. Data Sets Analysed and protocol deviations

Data sets analysed

The patient sets for this trial, will be presented by arm and overall, and are defined below:

- Screened Patients Set (SPS) will include all patients having signed the ICF,
- All Randomized Patients Set (ARPS) will include all patients having signed the inform consent form and randomized according to the assigned treatment arm,
- All Randomized and Treated Patients Set (ARTPS) will include all patients having signed the inform consent form, randomized according to the assigned treatment arm and treated in the trial,
- Full Analysis Set (FAS) will include all patients who have a valid primary criterion assessment, that is to say images available, with a perfusion CBV map considered as technically adequate (i.e., poor fair, good) and read. Patients will be analysed according to the treatment arm assigned at randomization. Two FAS will be considered in this study:
 - Off-site FAS taking into account off-site assessments for the two off-site readers,
 - On-site FAS: taking into account on-site assessments.
- Per-Protocol Set (PPS) will include all patients from the FAS who have no major protocol deviations and who have complied with the treatment allocated at randomization. Two PPS will be considered in this study:
 - Off-site PPS: all patients from the Off-site FAS and without major protocol deviations for both assessments and specific to the off-site assessment,
 - On-site PPS: all patients from the On-site FAS and without major protocol deviations for both assessments and specific to the on-site assessment,
- Safety Set (SS) will include all patients having received at least one injection of IMP regardless of the quantity. Patients will be analysed according to the treatment really received.

CONFIDENTIAL	STATISTICAL ANALYSIS PLAN N° GDX-44-016 VERSION N° 4.0 (REF I011622)	DATED: DECEMBER 20, 2024	F015830-03 Page 17 / 35
--------------	--	--------------------------	----------------------------

Table 2: Datasets analysed

	Screened Patient Set (SPS)	Safety Set (SS)	Full Analysis Set (FAS)		Per Protocol Set (PPS)	
			Off-site FAS	On-site FAS	Off-site PPS	On-site PPS
Disposition	✓					
Protocol Deviation	✓					
Population characteristics at baseline			✓		✓	
Exposure		✓				
Efficacy: Primary criterion			✓		✓	
Efficacy: Secondary criteria			✓	✓	✓	✓
Safety		✓				
Data Listings	✓					

Protocol deviations

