Imaging	Imaging acquisitions guidelines not respected with major impact on the primary criterion / Image technically not adequate at V2 according to off-site reader	Imaging QC (external vendors off site data)	Major for Off-site assessment
	Imaging acquisitions guidelines not respected with non-major impact on the primary criterion or on secondary criteria	Imaging QC (external vendors off site data)	Non major for Off-site assessment
Forbidden concomitant medication	Any contrast agent (MRI or CT) administered during the course of the trial or within 24 hours after the trial product administration	Clinical Database	Non major for both assessments
IMP deviation	Patient does not receive the IMP allocated by randomization on the IRT system and IMP is different from the one allocated	IWRS Database	Major for both assessments
	Patient does not receive the IMP allocated by	IWRS Database	Non major for both assessments

CONFIDENTIAL	STATISTICAL ANALYSIS PLAN N° GDX-44-016 VERSION N° 4.0 (REF I011622)	F015830-03 Page 20 / 35
--------------	--	----------------------------

Categorisation of the deviation	Protocol Deviation Coded Term	Source	Status
	randomization on the IRT system and IMP received is the same from the one allocated		
	The IMPs volume actually administered is different from the theoretical one from 5 to 10 % (relative difference)	Clinical database, IWRS database	Non major for both assessments
	The IMPs volume actually administered is different from the theoretical one by more than 10 % (relative difference)	Clinical database, IWRS database	Major for both assessments
	Injection rate <4 mL/sec	Clinical database	Major for both assessments
	The volume of saline flush injected is different from 20 mL	Clinical database	Non major for both assessments
	Temperature excursion for IMP	Monitoring	Non major for both assessments
	IMP management not appropriate	Monitoring	Non major for both assessments
Missing data	Blood sampling for Serum creatinine result and EGFR calculation is not performed at screening	Clinical Database	Non major for both assessments
	Pre-injection Axial 3D T1 weighted GRE sequence performed is not performed	Clinical Database	Non major for both assessments
	Pre-injection Axial 2D T2 weighted T(F)SE sequence performed is not performed	Clinical Database	Non major for both assessments
	Pre-injection Axial 2D Flair sequence performed is not performed	Clinical Database	Non major for both assessments

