5.5.2. Sensitivity analyses

Not Applicable.

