5.5.3. Supplementary analyses

Intra-reader variability at patient level

Intra-reader variability will be analyzed in a subgroup of 10% of patients randomly selected for whom the independent readers have re-read the images.

For the primary evaluation criterion, intra-reader variability will be studied using the Cohen kappa (κ) statistics. Agreement will be classified according to the value of the Cohen kappa statistics as described in the table below:

Table 4: Agreement according to Cohen kappa (κ) statistics

Cohen kappa statistics	Agreement
< 0.2	Poor agreement
$\geq 0.2 - \leq 0.4$	Fair agreement
$> 0.4 - \leq 0.6$	Moderate agreement
$> 0.6 - \leq 0.8$	Good agreement
$> 0.8 - 1.0$	Very good agreement

Inter-reader variability at patient level

Inter-reader variability will be evaluated on the whole set of trial patients, since each case will be read by the two independent readers.

The same methodology as the one presented above for intra-reader variability will be applied.

Diagnostic quality of CBV map assessed by on-site readers

The same methodology and analyses as the ones presented for the primary criterion will be applied to diagnostic quality of the CBV map according to the on-site readers.

CONFIDENTIAL	STATISTICAL ANALYSIS PLAN N° GDX-44-016 VERSION N° 4.0 (REF I011622)	F015830-03 Page 25 / 35
--------------	--	----------------------------

If the primary endpoint concluded to the non-inferiority of Elucirem versus Dotarem (off-site readers), then the non-inferiority will be tested for on-site readers: If the lower bound of the two-sided 95% CI is above the pre-stated margin of non-inferiority (-12%), Elucirem® will be declared non-inferior to Dotarem®.

In case of conclusion of non-inferiority of Elucirem® compared to Dotarem®, the superiority of Elucirem® compared to Dotarem® will then be tested in the same way as described above for the non-inferiority. No adjustment for multiplicity is needed as it is a simple closed testing procedure.

This secondary analysis will be performed on the On-site PPS and then on the On-site FAS and presented by arm only on one hand, and by arm and grade assigned at randomization on the other hand.

Quantification of the relative CBV for differentiating tumor grade (off-site assessment)

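### Both off-site efficacy sets drop maps that one reader calls non-diagnostic, and no planned analysis shows the non-inferiority result with those maps counted

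*SAP*

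**What the plan says.** SAP 2.2 sets the population: "Only for images considered technically adequate (i.e., poor, fair or good), the evaluation of primary and secondary criteria is performed". SAP 5.2 builds it into the sets: "Full Analysis Set (FAS) will include all patients who have a valid primary criterion assessment", meaning a map that is available, technically adequate and read. Protocol 7 and 11.3.2 carry the same restriction. SAP 5.5.1 adds the rule for two readers: a non-diagnostic rating "by at least one off-site reader, will be excluded from the Off-site FAS and Off-site PPS".

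The PPS is drawn from the FAS. SAP Table 3 also lists "Image technically not adequate at V2 according to off-site reader" within a deviation that is major for the off-site assessment.

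Protocol 8.4 introduces its list of adjudicated items with "The following criterion will be concerned by the consensus in case of discordance". That list, and the one in SAP 1.2, include diagnostic quality but not technical adequacy.

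Under "5.5.2. Sensitivity analyses" the SAP has only a not-applicable entry. On the set of all randomised and treated patients (ARTPS), it plans tables of technical adequacy and artifacts for the off-site readers. Tables 14.2.1.7 to 14.2.1.10, which report diagnostic quality, use only the Off-site PPS and FAS.

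**The concern.** The exclusion happens after randomisation and injection, and it is triggered by a rating of the image. Technical adequacy is a separate scale from the diagnostic quality under test, but a related one: a map that cannot be interpreted is of no diagnostic use to the patient who was scanned. Such a map leaves the denominator instead of counting as not good/excellent, and one unadjudicated rating is enough to remove it.

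A reader of the result will ask whether Elucirem yields a good or excellent map as often as Dotarem among patients who were scanned. If non-diagnostic maps are more frequent on Elucirem, the planned result is more favourable than the result with them counted. If they are more frequent on Dotarem, it is less favourable. PPS and FAS cannot show which, because both drop the same maps.

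**Working it through.** **Plan's own figure.** Inputs from SAP 3.3: 94% in both arms, margin 0.12, one-sided 2.5%, 80% power, unpooled Z. n = (1.960 + 0.842)² × 2 × 0.94 × 0.06 / 0.12² = 61.5, so 62 per arm (power 80.3%). 124 / 0.90 = 137.8, so 138, or 69 per arm. Both figures reproduce. The 14 extra patients are a drop-out allowance, not a forecast of non-diagnostic maps.

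**Lower bounds.** Non-diagnostic counts are assumed. About 94% of readable maps are taken as good/excellent. The interval is the planned Wald 95% CI with continuity correction:

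L = pE − pD − 1.96 × √[pE(1−pE)/nE + pD(1−pD)/nD] − 0.5 × (1/nE + 1/nD)

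For 2 vs 0, excluded: 63/67 vs 65/69, L = −0.0017 − 0.0791 − 0.0147 = −9.6%. Counted as failures: 63/69 vs 65/69, L = −0.0290 − 0.0864 − 0.0145 = −13.0%.

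| Non-diagnostic, Elucirem vs Dotarem (69 per arm) | Excluded | Counted as failures |
|---|---|---|
| 0 vs 0 | −9.2% | −9.2% |
| 1 vs 0 | −9.4% | −11.1% |
| 2 vs 0 | −9.6% | −13.0% |
| 2 vs 0, no continuity correction | −8.1% | −11.5% |
| 0 vs 2 | −9.2% | −7.2% |
| 2 vs 2 | −9.5% | −10.9% |
| 4 vs 4 | −9.8% | −12.1% |

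The 1 vs 0 case depends on n. At 62 per arm, 57/62 vs 58/62 gives −12.35%.

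**How often the planned rule passes when the all-treated difference is −12 points.** Simulation, 1,000,000 trials per scenario for the Elucirem-only and equal-rate rows, 69 per arm, Dotarem readable-map success 94%. Elucirem readable-map success is set to (0.94 × (1−qD) − 0.12)/(1−qE), where q is the non-diagnostic rate.

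| Non-diagnostic rate, Elucirem vs Dotarem | Planned rule passes |
|---|---|
| 2%, 4%, 6% vs 0% | 3.7%, 7.5%, 14.1% |
| 2% vs 1% | 2.4–2.5% |
| 3% vs 2% | 2.3% |
| 4% vs 2% | 3.4% |
| 6% vs 3% | 4.6% |
| Equal, 2%, 5%, 10% | 1.6%, 1.4%, 1.0% |

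Against the plan's own null among readable maps (82% vs 94%, equal rates of 0 to 10%), the planned test passes in 1.8–1.9%.

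**One-reader rule.** If each reader rejects r = 5% of maps with agreement κ, both reject r² + κr(1−r), and at least one rejects 2r minus that. For κ = 0.4: 2.15% and 7.85%. For κ = 0.8: 4.05% and 5.95%. Both r and κ are assumed.

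**The case against.** The best defence is that the population is declared, consistently, in both documents. Technical adequacy fails only when artifacts make the map uninterpretable. Readable but weak maps stay in, and a poor or fair diagnostic grade already counts as a failure. Off-site readers are blinded, and the core laboratory follows up image problems. An imbalance would show in the ARTPS tables. The failure-counted result can be derived from planned outputs: good/excellent counts from Table 14.2.1.9 over treated patients from Table 14.2.1.1. All of this stands. What is missing is that nobody has committed to the calculation, or to the handling of split ratings and missing maps, before seeing the data.

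The on-site analysis is a partial check. The set is defined by "On-site FAS: taking into account on-site assessments", and after off-site success "then the non-inferiority will be tested for on-site readers", so it can retain a map that an off-site reader rejected. But on-site reading is open-label, uses each site's own software and has its own adequacy exclusion.

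A reader might infer that the primary test is invalid, that the exclusion favours Elucirem, or that the false-positive rate is 14%. The documents support none of these. They give no non-diagnostic rate and do not say that it depends on the agent, although T2* artifacts are a listed cause and a contribution cannot be ruled out. The 14.1% needs 6% non-diagnostic maps on Elucirem and none on Dotarem. The 2 vs 0 flip disappears without the continuity correction, and any two extra Elucirem failures would produce the same −13.0%, so it partly reflects limited power.

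**Conclusion.** The gap is real but limited. The planned test answers its declared question, with about 1.8% error at the readable-map null. It does not show whether the conclusion extends to scanned patients whose map was rejected, and nothing else planned gives that estimate with a confidence interval.

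The size depends wholly on assumed rates. There is no inflation with equal rates, little at modest imbalances (2.3–4.6%), and more only when rejections fall on Elucirem alone. At 69 per arm, with the continuity correction, two such maps could change the verdict; at 62 per arm, one could. If no maps are non-diagnostic, the effect of this rule is nil. This is a cheap transparency improvement, not an error in the primary test.

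**What to change.** Replace the entry in SAP 5.5.2 with one supportive analysis, fixed before database lock:

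- **Set and method:** ARTPS patients by randomised arm, with the same 95% CI and −12% as reference.
- **Main rule:** a map rated non-diagnostic by at least one off-site reader counts as not good/excellent.
- **Variant:** a map rejected by only one reader takes the other reader's grade. The SAP should confirm that the accepting reader still grades such maps.
- **Missing maps:** those missing for reasons that could relate to the injection or the agent count as not good/excellent. Those missing for purely logistical reasons are left out and reported by arm with the reason.
- **Reporting:** give the between-arm difference in non-diagnostic rate with a CI, and state that the primary conclusion applies to patients with technically adequate maps.

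The cost is SAP text and a few tables. The set exists, and each reader's adequacy rating is already listed (Listing 16.2.6.1).

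There are three statistical downsides:

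- **Power:** with 94% readable-map success in both arms and equal non-diagnostic rates of 2%, 5% and 10%, this analysis passes with probability 0.65, 0.54 and 0.42, against 0.73, 0.73 and 0.70 as planned. It would fail where the primary succeeds in about 12%, 23% and 32% of trials, so it must not act as a gate.
- **Dilution:** equal non-diagnostic rates shrink a true readable-map difference. At 82% vs 94% it passes in about 2.2% (5% non-diagnostic) and 2.6% (10%), against 1.8% as planned.
- **Precision:** the CI for the rate difference is wide. By Newcombe's method, 2/69 vs 0/69 gives 2.9 points (−2.8 to 10.0).

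It should therefore be read beside the primary result and the non-diagnostic rates, never alone.

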11.2 Sample Size

Sample sizes of 62 in each arm achieve 80% power to detect a difference of 0 when the non-inferiority difference is -0,12. The reference group proportion is 94% [17]. The treatment group proportion is assumed to be 82% under the null hypothesis. The power was computed for the case when the actual treatment group proportion is 94%. The test statistic used is the one-sided Z test (unpooled). The significance level of the test is 2.5% (unilateral, 5% bilateral).

Assuming a 10% drop-out rate is expected, the sample size increases to 138 patients to test that the proportion of patients presenting with images of excellent and good quality in the Elucirem[®] arm is not inferior to the proportion of patients presenting with images of excellent and good quality in the Dotarem[®] arm.

The calculations for determine the sample size were performed using the PASS statistical software.

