11.3.6.1 Primary analysis

The primary endpoint of the trial is the proportion of patients presenting with images of excellent and good quality, according to off-site readers, in the Elucirem® and the Dotarem® arm.

At the final analysis, non-inferiority will be assessed by calculating the difference in proportion between Elucirem® and Dotarem® arms, and by constructing a two-sided 95.2% CI around this difference. If the lower bound of the two-sided 95.2% CI is above the pre-stated margin of non-inferiority (-12%), Elucirem® will be declared non-inferior to Dotarem®.

The Wald test statistic with a continuity correction will be used.

In case of conclusion of non-inferiority of Elucirem® compared to Dotarem®, at the final analysis, the superiority of Elucirem® compared to Dotarem® will then be tested in the same way as described above for the non-inferiority. No adjustment for multiplicity is needed as it is a simple closed testing procedure.

The primary analysis will be performed on the PPS and then on the FAS.

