3.3. Determination of sample size

Sample sizes of 62 in each arm achieve 80% power to detect a difference of 0 when the non-inferiority difference is -0.12. In the reference arm (Dotarem®), the proportion of patients presenting with CBV map of excellent and good diagnostic quality is 94% [1]. In the Elucirem® arm, this proportion is assumed to be 82% under the null hypothesis. The power was computed for the case when the actual treatment arm proportion is 94%. The statistical test used is the one-sided Z test (unpooled). The significance level of the test is 2.5% (unilateral, 5% bilateral).

Assuming a 10% drop-out rate, the sample size increases to 138 patients to test that the proportion of patients presenting with images of excellent and good quality in the Elucirem® arm is not inferior to the proportion of patients presenting with images of excellent and good quality in the Dotarem® arm.

The sample size was calculated using the PASS statistical software by Exystat.

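### The 80% power at 62 per arm belongs to an uncorrected Z test; the specified continuity-corrected Wald test has less, about 68% if the correction is the standard one

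*SAP*

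**What the plan says.** **Sample size.** SAP 3.3 states: "Sample sizes of 62 in each arm achieve 80% power to detect a difference of 0 when the non-inferiority difference is -0.12". The reference proportion is 94%. For Elucirem, "this proportion is assumed to be 82% under the null hypothesis", and power is calculated at a true 94%. The test is named there: "The statistical test used is the one-sided Z test (unpooled"), at one-sided 2.5%. Protocol 11.2 uses the same inputs and the same test, and the Protocol synopsis repeats them. A 10% drop-out allowance takes 124 evaluable patients to 138 enrolled. None of these three places mentions a continuity correction.

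**Primary analysis.** SAP 5.5.1 states: "The Wald statistical test with a continuity correction will be used". Protocol 11.3.6.1 agrees: "The Wald test statistic with a continuity correction will be used". Under SAP 5.5.1, non-inferiority is declared when the lower limit of the two-sided 95% confidence interval for the difference lies above -12%. The analysis is done on the Off-site PPS and then on the Off-site FAS.

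The form of the correction is not given anywhere. No section gives power for the corrected test or explains why the planning and analysis tests differ.

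**The concern.** A continuity correction moves the lower confidence limit down by a fixed amount. For any data set it makes non-inferiority harder to declare, so it must cost power relative to the uncorrected test. At 62 per arm the standard correction is 1/62, or 1.6 percentage points, which is more than an eighth of the 12-point margin.

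Two things are at stake:

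- **The power claim.** If non-inferiority is not shown, a reader will judge that result against a stated 80% chance of success that the specified test does not have.
- **The missing formula.** The size of the correction is part of the primary decision rule. Left open, it can settle a close result after the data are in.

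**Working it through.** **Inputs.** SAP 3.3 and Protocol 11.2 give 94% in both arms under the alternative, 82% vs 94% under the null, margin 0.12, one-sided 2.5% and 62 per arm. SAP section 4 confirms one-sided 2.5% at the final analysis now that the interim analysis has been dropped. Allocation is 1:1.

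**Step 1: reproduce the plan's figures without a correction.**

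- n per arm = (1.960 + 0.8416)² × 2 × 0.94 × 0.06 / 0.12² = 61.5, so 62.
- SE at 62 per arm = √(2 × 0.94 × 0.06 / 62) = 0.04265.
- Power = Φ(0.12/0.04265 − 1.960) = 80.3%.
- Enrolment = 124/0.9 = 137.8, so 138.

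All the stated figures come out, so the sizing used no correction.

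**Step 2: apply a correction.** The form is an assumption, because the documents give none. The standard form is (1/n1 + 1/n2)/2, which is 1/n with equal arms. A correction of half that size is shown as a second case to give a range. With a correction of c/n, where c = 0 (none), 0.5 (half-size) or 1 (standard):

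Power = Φ((0.12 − c/n)/SE − 1.960)

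At 62 per arm:

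- half-size: Φ((0.12 − 0.0081)/0.04265 − 1.960) = 74.7%
- standard: Φ((0.12 − 0.0161)/0.04265 − 1.960) = 68.3%

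**Step 3: check by exact binomial enumeration.** The confidence-interval rule was applied to every possible pair of counts. Power is at 94% vs 94%. Error is the one-sided probability of declaring non-inferiority at 82% vs 94%.

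| Per arm | Correction | Approximate power | Exact power | Exact error |
|---|---|---|---|---|
| 62 | none | 80.3% | 82.1% | 3.6% |
| 62 | half-size | 74.7% | 75.9% | 2.6% |
| 62 | standard | 68.3% | 68.6% | 1.6% |
| 69 | none | 84.3% | 84.2% | 3.4% |
| 69 | half-size | 79.6% | 79.2% | 2.6% |
| 69 | standard | 74.2% | 75.2% | 1.9% |

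The 69-per-arm rows suppose that all 138 enrolled patients are evaluable. Under the standard form, 80% power would need 78 evaluable per arm (80.5% approximate, 80.3% exact).

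**Step 4: a close result.** Take 58/62 on Dotarem and 57/62 on Elucirem. The difference is −0.0161 and its SE is 0.0466. The lower limit is −0.107 with no correction, −0.115 with the half-size one and −0.124 with the standard one. Against −0.12, the first two pass and the third fails.

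**The case against.** The best case against the point is about its weight.

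- **The direction is conservative.** For given data the correction only makes the claim harder, so the sponsor bears the cost. This stands, and it is why the point concerns stated power and not validity. The error rates above hold at 82% vs 94% only. With the standard correction at 62 per arm, the exact error is 1.5% at 78% vs 90%, 2.4% at 86% vs 98% and 3.3% at 87% vs 99%.
- **The 68% is conditional.** No document gives the correction's size, and the half-size form is only an illustration. This stands for the exact figure. It does not rescue the 80%: any positive correction lowers power, and both forms computed fall clearly short at 62 per arm. The missing formula is itself part of the defect.
- **The 94% assumption matters as much.** With the standard correction at 62 per arm, exact power is 76% if both proportions are 95% and 83% if both are 96%. True, but the plan ties its 80% to 94%, and at 94% the figure is wrong for the specified test.
- **The drop-out allowance absorbs the gap.** It does so only in part. The allowance exists to deliver 62 evaluable per arm. Even with no losses, the standard form gives about 75%.
- **The close-result example is one patient wide.** With 58/62 on Dotarem, neighbouring Elucirem counts give the same non-inferiority verdict under all three forms. The example shows that the formula can decide the outcome, not that it probably will.
- **Recruitment is probably complete.** SAP section 4 implies this. It limits the remedy to wording but does not make the stated power correct.

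**Conclusion.** The concern holds. The planning test and the primary analysis test differ, and the 80% belongs to a test that the plan does not use. At 62 per arm and 94% in both arms, the specified test has about 68% power under the standard correction, roughly 12 points below the claim, or about 75% under a half-size one. The matching chances of missing non-inferiority are 31-32% and 24-25%, against an implied 20%. If all 138 patients were evaluable, the half-size case would be only just below 80% (79.6%, exact 79.2%), while the standard case would be about 75%. The size of the Off-site PPS cannot be known in advance.

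That power at 62 per arm falls short under either form is firm. The 68% rests on the correction being (1/n1 + 1/n2)/2 and on true proportions of 94%. At the planning null the standard correction keeps the exact error below 2.5%, so this should be fixed as a misstated power and an incomplete test specification.

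**What to change.** 1. In SAP 5.5.1, write out the continuity-correction formula, before database lock if that is still possible.
2. In the Protocol synopsis, Protocol 11.2 and SAP 3.3, give the power of the specified test. If the correction is the standard one, that is about 68% at 62 evaluable per arm and about 75% at 69. If it is another form, quote the power for that form.
3. Keep the pre-specified test. Deleting the correction to recover 80% would be the wrong repair, because the uncorrected test has an exact one-sided error of 3.6% at 82% vs 94%.

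A Newcombe interval could be added as a sensitivity analysis (SAP 5.5.2 lists none), but this repair does not need it and it should not replace the primary test.

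The cost is wording in four places and a less favourable power statement. The primary test, margin and number of patients do not change. If the documents can no longer be amended, put the formula and the restated power in the study report.
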